11.3 Abnormal BCG Injection Site Procedures

The BCG injection site evaluations are scheduled from Day 0 to 84±3. However, signs of an abnormal injection site may present around Day 28. If an injection site does not have a well healed scar, or has an open and draining ulcer, then the subject will be asked to return to the clinic twice per/week from the time the abnormality is identified until it has resolved. At each of these visits the following evaluations will be completed: assessments of the ID challenge site, assessments for lymphadenopathy if indicated based on review of interim medical history and clinical assessment, as well as review AEs/SAEs, concomitant medications, and health status, and collect and dispose of returned biohazard materials. Photographs will be taken once per/week from the day of the abnormal assessment until it has resolved.

11.4 Withdrawal Procedures

Participants who discontinue from the study will be asked to complete visits 14-17. Visits 14-17 will occur using the same chronology as in the procedures schedule. If a female becomes pregnant, PBMC will not be collected on visit 17. However, PBMC will be collected from all other participants. If the participant refuses to complete visits 14-17, they will be asked to complete visit 17 which should occur at least 7 days, but \leq 30 days, after the dose of BCG.

Procedures to be performed on visits 14-17: see above in section 11.2 Clinic Visit Schedule.

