- Blood will be collected for ELISPOT/ICS and additional assays to assess the integrity of the immune system on Days: 0, 8±1, 28±1, 56±2, 84±3, and 114±1. Whole blood will be collected for RNA seq studies on Days: 0, 1, 2, 3, 4, 8±1, 15±1, 28±1, 56±2, and 84±3. Plasma obtained from the density gradients used to purify PBMCs will be collected and frozen on Days: 0, 1, 8±1, 15±1, 28±1, 56±2, 84±3, and 114±1. Anticoagulated whole blood will be collected for dendritic cell (DC), monocyte and natural killer (NK) cell assays on Days: 1, 4, 8±1, 15±1, 28±1, 56±2, and 114±1.

10.7 **Photographs**

Photographs of the ID challenge site will be taken at each follow-up visit after Tice® BCG administration starting on Day 4 through Day 56±2. If the participant has any abnormality and does not have a well-healed scar, or the site is open and/or draining, photographs will continue once/week from the day the abnormality was identified until it has resolved. All subjects will have a final photograph of the ID challenge site on Day 114±1 or upon early termination.

10.8 **PPD Skin Test**

2-Step PPD skin test will be performed and/or accessed on Days: 98±1, 100±1, 112±1 and 114±1. If the first PPD skin test result is negative, then the second PPD skin test will be performed 2-4 weeks later. If either of the 2-Step PPD skin test results is positive, defined as ≥ 10 mm of induration, then the subject will have a QuantiFERON®-TB Gold Test performed to determine TB infection or BCG immunity.

10.9 **Memory Aid eCRF Device and AE/SAE Recording Training**

Participants will be instructed on how to use the initial and on-going subject memory aids eCRF device and how to measure and record AEs/SAEs, concomitant medication and other health status information.

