 - Unsolicited AEs/SAEs recorded Days 1-114,
 - Concomitant medications recorded Days 1-114.
- Collection of used dressing/gauze.

Days 4 (clinic visit 6), 5 (clinic visit 7), 6 (clinic visit 8), 8 ± 1 (clinic visit 9), 15 ± 1 (clinic visit 10), and 28 ± 1 (clinic visit 11)

- INH dosing days 4, 5, and 6 only: For the 5 participants assigned to Group 1, they will take INH: oral tablets of either three 100mg tablets (total 300mg) or one 300mg tablet for 3 days post BCG dosing,
- Days 8 ± 1 (clinic visit 9) and 15 ± 1 (clinic visit 10) only: Repeat skin biopsy,
- Assess ID challenge site,
- Review health status and AEs/SAEs that were recorded on the memory aid eCRF device,
- Review concomitant medications,
- Assess for lymphadenopathy if indicated based on review of interim medical history and clinical assessment,

- Targeted physical exam and clinical assessment may be performed if indicated based on review of interim medical history, reactogenicity (as applicable),
- Blood draws via venipuncture for immunogenicity and mycobacteria assays:
 - Day 4: 6.5mls (1.5 tsp),
 - Day 8±1: 74.5mls (5 tablespoons (tbs)),
 - Day 15±1: 56.5mls (4 tbs),
 - Day 28±1: 94.5mls (6 tbs),
- Collect used dressing/gauze,
- Photograph of ID challenge site.

Days 16-114±1

- On-going participant self-evaluations that will be recorded on their memory aid eCRF device for pain, tenderness and drainage. Participants can record their temperature if taken.

Days 56±2 (clinic visit 12) and 84±3 (clinic visit 13)

- Day 56±2 (clinic visit 12) only: Repeat skin biopsy
- Assess ID challenge site (if an abnormal BCG injection site is identified see Abnormal BCG Injection Site Procedures in section 11.3),
- Review health status and AEs/SAEs that were recorded on the memory aid eCRF device,
- Review concomitant medications,
- Assessments for lymphadenopathy if indicated based on review of interim medical history and clinical assessment,
- Targeted general exam and clinical assessment may be performed if indicated based on review of interim medical history, reactogenicity (as applicable),
- Blood draws via venipuncture for immunogenicity and mycobacteria assays:
 - Day 56±2: 94.5mls (6 tbs)
 - Day 84±3: 94.5mls (6 tbs)
- Collect used dressing/gauze,
- Photograph of ID challenge site.

Day 98±1 (clinic visit 14)

- Assess ID challenge site,
- Review health status and AEs/SAEs that were recorded on the memory aid eCRF device,
- Review concomitant medications,

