- Blood draw via venipuncture for diagnostic assays: 4mls (1 tsp),
- PPD skin test.

Day 100±1 (clinic visit 15)

- Assess ID challenge site,
- Review health status and AEs/SAEs that were recorded on the memory aid eCRF device,
- Review concomitant medications,
- PPD skin test assessment.

*Day 120/134: If the first PPD skin test result is negative, then the second PPD skin test will be performed 2-4 weeks later. If either of the 2-Step PPD skin test results is positive, defined as ≥ 10

mm of induration, then the participant will have a QuantiFERON®-TB Gold Test performed to determine TB infection or BCG immunity.

Days 112±1 (clinic visit 16)

- Assess ID challenge site,
- Review health status and AEs/SAEs that were recorded on the memory aid eCRF device,
- Review concomitant medications,
- Blood draw via venipuncture for diagnostic assays: 4mls (1 tsp),
- PPD skin test.

Day 114±1 (clinic visit 17) End of Study

- General exam,
- Assess ID challenge site,
- Review health status and AEs/SAEs that were recorded on the memory aid eCRF device,
- Review concomitant medications,
- Blood draw via venipuncture for immunogenicity and humoral assays: 138mls (9.5 tbs),
- Photograph of ID challenge site,
- PPD skin test assessment,
- Participants returns memory aid eCRF devices.

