14.0 SUBJECT DISCONTINUATION OF ACTIVE TREATMENT

Subjects may voluntarily withdraw their consent for study participation at any time and for any reason, without penalty.

A subject may be withdrawn from the study for the following reasons:

- The subject withdraws consent,
- The subject develops a medical disease or condition, or any new clinical findings for which continued participation, in the opinion of the site principal investigator or appropriate sub-investigator, would compromise the safety of the subject, would interfere with the subject's successful completion of this study, or would interfere with the evaluation of responses,
- The subject fails to comply with the scheduled study visits,
- The study is terminated,
- Any reason that, in the opinion of the investigator, precludes the subject's continued participation in the study,
- The subject becomes pregnant.

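### Section 11.4 times the fallback exit visit at Days 7-30 after BCG, so a participant who leaves after Day 30 and declines visits 14-17 has no date on which it can be held

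*Combined protocol and SAP*

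**What the plan says.** Section 11.4 (Withdrawal Procedures) has two steps. By default, a participant who discontinues is asked to complete visits 14-17: "Visits 14-17 will occur using the same chronology as in the procedures schedule". Appendix B places those visits at Days 98, 100, 112 and 114. If the participant refuses them, the fallback is visit 17 alone: "they will be asked to complete visit 17 which should occur at least 7 days" and no more than "30 days, after the dose of BCG".

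Other sections bear on that window:

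- Sections 10.3 and 11.2: one intradermal BCG dose, given on Day 0 (visit 2).
- Section 14.0: "Subjects may voluntarily withdraw their consent for study participation at any time and for any reason, without penalty". The investigator may also withdraw a participant, for example because "The subject fails to comply with the scheduled study visits".
- Section 11.2: procedures continue well past Day 30, including "Day 56±2 (clinic visit 12) only: Repeat skin biopsy". The planned date of visit 17 is "Day 114±1 (clinic visit 17) End of Study".
- Section 15.3: AEs are documented to Day 56±2 and SAEs to Day 114±1.
- Section 10.7: "All subjects will have a final photograph of the ID challenge site on Day 114±1 or upon early termination".

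**The concern.** The fallback visit is counted from the dose, but the event that triggers it is discontinuation, which can happen at any point up to Day 114. A window that closes on Day 30 serves early leavers only. No other section gives a different window for late leavers.

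Every participant is a healthy volunteer given live BCG, with biopsies of the challenge site up to Day 56. For someone who declines visits 14-17, the single exit visit is the only clinic check that 11.4 requests. It carries the general exam, the site assessment and the AE/SAE review. A late leaver needs that check as much as an early one, yet for the late leaver the protocol gives staff no usable timing.

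**Working it through.** No power or alpha formula applies; this is calendar arithmetic.

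**Inputs.** Dose on Day 0 (10.3, 11.2). Lower bound 7 days and upper bound 30 days after the dose (11.4). Visits 11, 12 and 13 on Days 28, 56 and 84, and visit 17 on Day 114 (11.2, Appendix B).

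**Window as written.** Day 0 + 7 = Day 7 to Day 0 + 30 = Day 30. For a participant who leaves on Day x, the possible dates run from max(7, x) to 30. This is empty once x > 30.

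| Leaves on day | Possible dates as written | Position |
|---|---|---|
| 15 | 15-30 | open |
| 28 | 28-30 | 30 − 28 = 2 days left |
| 31 | none | 31 − 30 = 1 day past |
| 56 | none | 56 − 30 = 26 days past |
| 84 | none | 84 − 30 = 54 days past |

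AE documentation runs to Day 56, so its last 56 − 30 = 26 days lie after the window. SAE documentation continues for 114 − 30 = 84 days after it.

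**Window counted from discontinuation, with limits.** From max(7, x) to the earlier of x + 30 and Day 114 (±1). Leaving on Day 3 gives Days 7-33; Day 31 gives 31-61; Day 56 gives 56-86; Day 84 gives 84-114; Day 98 gives 98-114. It is never empty.

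**Blood volume at a moved visit.** Section 11.2 gives 138 mL for visit 17. The 56-day totals in Appendix A are 395 mL at Day 28, a peak of 489.5 mL at Day 56, and 283.5 mL at Day 84. On nominal days, with all earlier draws taken:

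- Days 28-30 (allowed now): 395 + 138 = 533 mL.
- Days 31-55, before any Day 56 draw: also 533 mL. Staying within the planned peak leaves 489.5 − 395 = 94.5 mL.
- Day 56, after the visit 12 draw: 489.5 + 138 = 627.5 mL. Nothing is left under the peak.
- Day 57: the screening and Day 0 draws (29 + 114.5 = 143.5 mL) drop out of the 56-day span, so 489.5 − 143.5 + 138 = 484 mL, which fits.
- Day 84, after the visit 13 draw: 283.5 + 138 = 421.5 mL, which fits.

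The documents state no blood-volume limit. The planned peak serves here only as a benchmark.

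**PPD.** Visit 17 reads a test placed at visit 16. A participant who comes only for the fallback visit has no test to read.

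**The case against.** The case for leaving the text alone is that the clause is a request (*asked*, *should*), applies only after the default visits are refused, and concerns a study of 10. Staff may see a late leaver on any date. Known problems are covered elsewhere: 11.3 follows an abnormal site until it resolves, 15.2.1 follows AEs to resolution, 15.2.4 follows SAEs to resolution or stabilization, and self-reports go through a REDCap survey (10.6.2). All of this stands and is why the point is minor. It does not supply a date for the visit.

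It can also be said that the dose was the intended anchor, perhaps to standardise post-dose sampling in early leavers. The documents do not state the intent, so this cannot be excluded. Even then, late leavers have no possible date.

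Several stronger readings are tempting but unsupported:

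- A reader might infer that the final photograph also has no valid date. Section 10.7 times it at early termination, independently of 11.4.
- A reader might take 84 of 114 follow-up days (74%) as the share of participants exposed. It is a share of the calendar. It also counts Days 98-114, when the participant is already within visits 14-17 and the planned visit 17 is close.
- A reader might find the default visits' chronology ambiguous between study days and spacing. The clause refers to the procedures schedule, and Appendix B fixes the days.
- A reader might infer that the primary safety endpoint is compromised. AEs and SAEs are summarised descriptively (18.1), and a late leaver has already been followed beyond Day 30. What may be lost is a final check.

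**Conclusion.** The rule fails when followed. For anyone who leaves after Day 30 and declines visits 14-17, the fallback window has already closed, by 26 days at the Day 56 visit and 54 days at the Day 84 visit. This rests only on the single Day 0 dose and the stated bounds, not on any view of what the authors intended.

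It is a minor participant-safety correction. The documents give no withdrawal rate, and with N=10 the number affected may be zero. Nothing bars staff from seeing such a participant, and sample size, randomization, power and analysis are untouched. It is worth correcting because the participants are healthy volunteers given a live organism and the change is a short one.

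**What to change.** In section 11.4, replace the timing of the fallback visit with wording to this effect: *at discontinuation or within 30 days after it, no earlier than 7 days after the BCG dose and no later than Day 114±1.*

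State what the visit contains:

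- general exam, challenge-site assessment, and lymph node check if indicated;
- AE/SAE and concomitant medication review;
- the section 10.7 photograph, if not already taken at termination;
- no PPD reading if no test was placed;
- the 138 mL draw reduced or omitted if it would take the 56-day blood volume above the planned peak of 489.5 mL. On nominal days this means at most 94.5 mL for Days 28-55 and none on Day 56 itself if the visit 12 draw was taken; the full draw fits from Day 57.

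**Cost.** One wording amendment with IRB approval. The fallback stays a single visit that is already requested, so none is added. Leavers' visit 17 samples will fall on more varied days, and some will be smaller or missing. They feed only secondary data that section 18.1 analyses descriptively.

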12.0 LABORATORY TESTING AND ASSAY SCHEDULE

See Appendix A for Laboratory Procedures Table.

13.0 SAFETY MONITORING COMMITTEE

A Safety Monitoring Committee (SMC) will be convened periodically by Fred Hutch to review participant safety data, which may include solicited and unsolicited AEs/SAEs, concomitant medications, clinical laboratory values and any physical examinations. Interim statistical reports may be generated as deemed necessary. The SMC may receive data in aggregate and presented by group. As an outcome of each review, the SMC will make a recommendation at that time as to the advisability of proceeding with Tice® BCG administration, and to continue, modify or terminate the study.

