1.0 PROTOCOL SYNOPSIS

Protocol Title	A Phase I single site open label clinical trial for the development of a human BCG challenge model to assess TB drugs and vaccines
Trial Phase	Phase 1
Study Objectives	
Primary:
 
 Evaluate the safety and tolerability of Intradermal Tice® BCG followed by a short course (3 days) of isoniazid (INH). Assess the BCG bacterial burden in skin biopsies as measured by culture. 
Secondary:
 
 Assess the BCG bacterial burden in skin biopsies as measured by a novel qPCR assay. Evaluate peripheral blood cellular frequencies (Trucount) after intradermal BCG. Evaluate adaptive immune response after intradermal BCG (validated intracellular cytokine staining after stimulation). 
Exploratory
 
 To conduct analyses related to furthering the understanding of TB, immunology, vaccines, and clinical trial conduct.
Outcome Measures	
Primary Endpoints:
 
 The rate of AE's/SAE's Colony forming units (CFU) from culture 
Secondary Endpoints:
 
 Quantitative bacterial 16S ribosomal DNA PCR Microbial viability testing pre-ribosomal RNA RT-PCR Humoral and cellular immune responses after BCG immunization
Summary of Study Design	This is phase 1, open-label, randomized clinical protocol to develop a human challenge model using the licensed and available BCG VACCINE USP (TICE® strain) with and without antibacterial Isoniazid (INH). It will involve 10 participants who will be screened and consented, given an intradermal injection of BCG; five of these participants will receive oral INH for 3 days. Participants will undergo physical exams, clinical evaluations, blood draws, urine collections, skin biopsies, and pregnancy tests. This study will measure the rate of replication by utilizing qPCR and in vitro culture, systemic innate and adaptive immune responses, including humoral and cellular assay analyses and the evaluation and PPD/IGRA status.
Population	10 healthy male and non-pregnant female individuals, HIV and TB uninfected, aged 18 to 45 years, with no extensive residence in high TB endemic country.

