Drugs	
 BCG VACCINE USP (TICE® strain) has been licensed for percutaneous use and is an attenuated, live culture preparation of the Bacillus of Calmette and Guerin (BCG) strain of Mycobacterium bovis. Isoniazid is a licensed antibacterial available as 100mg and 300mg tablets for oral administration.
Dose	Ten participants will receive one intradermal injection of 2×10^6 cfu Tice® BCG (ID), and five of these participants will receive oral tablet(s): either three tablets of 100mg or one tablet of 300mg of INH each day for 3 days following the injection of BCG vaccine.
Duration of Participation	16 to 24 weeks (screening up to 8 weeks prior to enrollment, study follow up for 16 weeks after enrollment)

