10.3 Group Assignment

After the participant meets enrollment criteria, they are randomly assigned by a computer program to 1 of the 2 groups. In both groups, participants will be immunized intradermally with a single dose of 2×10^6 cfu Tice® BCG.

- Group 1 subjects will receive INH dosages on Days 4, 5, and 6.
- Group 2 (control arm) will not receive INH.

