10.4 Study Drug Administration

Tice® BCG and INH preparations will be performed by the participating clinical study site pharmacist and administration will be performed by a study clinician licensed to administer study product.

10.4.1 *BCG injection (all participants)*

One intradermal injection of Administration of BCG 2×10^6 cfu Tice® BCG in the deltoid region, Following administration of Tice® BCG, intradermal (ID) site reactions will be assessed for at least 30 minutes.

10.4.2 *INH (Group 1 only)*

For the 5 participants assigned to Group 1, they will take INH: oral tablets of either three 100mg tablets (300mg) or one 300mg tablet on days 4, 5, and 6 post BCG dosing.

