16.0 DATA AND SAFETY MONITORING PLAN

The Data Safety Monitoring Plan for this study includes the Safety Monitoring Committee (SMC) noted in Section 13.0 above and the safety assessments noted in Section 15.0. As this is an observational study using licensed products consistent with product labeling, external monitoring and a chartered committee with independent representation is not required.

The protocol will be reviewed at least annually and as needed by the Institutional Review Board (IRB). The IRB reviews the study progress and safety information to assess continued acceptability of the risk-benefit ratio for human subjects. Approval of committees as applicable is necessary to continue the study. The study investigators will monitor for adverse events and will refer participants for local medical care if necessary.

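### Section 16.0 waives independent monitoring on two premises that the protocol's own text contradicts, and nothing ties a Safety Monitoring Committee review or a pause to BCG dosing

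*Combined protocol and SAP*

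**What the plan says.** **Oversight level.** Section 16.0 states that "external monitoring and a chartered committee with independent representation is not required". The only reason it gives is this: "As this is an observational study using licensed products consistent with product labeling".

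**Design.** The synopsis (Section 1.0) reads: "This is phase 1, open-label, randomized clinical protocol to develop a human challenge model". Section 10.3 says of eligible participants that "they are randomly assigned by a computer program to 1 of the 2 groups".

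**Product and route.** The synopsis says "BCG VACCINE USP (TICE® strain) has been licensed for percutaneous use". Section 10.3 says "In both groups, participants will be immunized intradermally with a single dose", and Section 10.4.1 repeats the route: "One intradermal injection of Administration of BCG". Section 5.5 calls the BCG dose on-label but does not say that the intradermal route is.

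**The SMC.** Section 13.0 reads: "A Safety Monitoring Committee (SMC) will be convened periodically by Fred Hutch to review participant safety data". After each review the committee is to recommend whether BCG administration should go on and whether the study should continue, change or stop. Section 15.2.4 sends SAEs to the SMC on the same periodic basis and sends related, unexpected SAEs to the IRB as well. Section 16.0 adds IRB review at least once a year and as needed.

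**Dosing window.** Ten participants receive one BCG dose each (Sections 6.2 and 10.3), and enrollment is to take two months (Section 7.0).

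**The concern.** There are two linked problems.

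First, the choice of oversight rests on a description of some other study. A trial that randomizes healthy volunteers, injects all of them with live BCG and gives half of them isoniazid is interventional. The claim of consistency with labeling conflicts with the protocol's own account of the licensed route. If both premises fall, Section 16.0 gives no reason for the level of monitoring chosen.

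Second, advice on whether to proceed with BCG has effect only while someone remains to be dosed. With one dose per participant and a short enrollment window, that period is brief. Without a date, an enrollment milestone or an event trigger, a site could follow the protocol to the letter and still hold its first SMC meeting after the tenth dose. The same holds after a related SAE: the text requires neither a prompt SMC meeting nor a hold on the next dose.

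**Working it through.** **1. The premises against the text**

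| Premise in 16.0 | What the protocol says elsewhere | Result |
|---|---|---|
| Observational | Randomized phase 1 challenge (1.0, 10.3); BCG for all, isoniazid for five (10.4) | Contradicted |
| Consistent with labeling | Licensed route given as percutaneous (1.0); intradermal injection used (10.3, 10.4.1); dose alone called on-label (5.5) | In conflict as to route; the label itself is not supplied |

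**2. The plan's own safety arithmetic**

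No figure in the plan bears on SMC timing. The nearest is the table in Section 18.1, and it reproduces. At a true rate of 25%, 1 − 0.75^5 = 0.763 for at least one event in five, and the chance of at least two is 0.367 (stated 0.76 and 0.37).

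**3. Doses given before a first SMC meeting**

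Inputs: ten single doses; a two-month window taken as T = 60 days; even spacing (assumed), so dose k falls on day (k − 1) × T/9. Meeting dates are assumed because the plan gives none. T = 30 is a sensitivity case, faster than the stated window.

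| First meeting on day | 28 | 42 | 56 | 84 |
|---|---|---|---|---|
| Dosed, T = 60 | 5 | 7 | 9 | 10 |
| Dosed, T = 30 | 9 | 10 | 10 | 10 |

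At the tenth dose (day 60 when T = 60), 7 participants have reached Day 15, 5 have reached Day 28 and 1 has reached Day 56.

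**4. What one required review would do**

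Example: review at the fifth participant's Day 15, required before the eighth dose. With T = 60 the fifth dose falls on day 4 × 60/9 = 26.7 and the eighth on day 7 × 60/9 = 46.7. The Day 15 visit falls on day 41.7, when seven have been dosed and three have reached Day 28 (the third on day 13.3 + 28 = 41.3). At least three doses stay open to advice; the present text guarantees none.

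**5. The delay it causes**

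Hold on the eighth dose = max(0, d5 + 15 + L − d8), where d5 and d8 are the days of the fifth and eighth doses and L is the SMC turnaround in days (assumed). With even accrual and T = 60 this is max(0, L − 5). For random accrual, ten dosing days were drawn uniformly over 60 days, 400,000 times.

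| Turnaround L (days) | 0 | 5 | 7 | 14 |
|---|---|---|---|---|
| Even, T = 60 | 0 | 0 | 2 | 9 |
| Even, T = 30 | 5 | 10 | 12 | 19 |
| Random, 60 days: mean | 2.4 | 5.4 | 6.9 | 12.9 |
| Random, 60 days: 90th percentile | 8 | 13 | 15 | 22 |

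Using the fourth participant's Day 15 (day 20 + 15 = 35), the even 60-day hold is max(0, L − 11.7): 0 days at L = 7 and 2.3 at L = 14. The random-accrual means are 3.5 and 8.2 days. That review has Day 28 data on two participants rather than three.

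**6. How often an SAE pause would occur**

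For a related-SAE rate p (assumed), the chance of at least one among the nine dosed before the last is 1 − (1 − p)^9: 0.09, 0.17 and 0.37 at p = 1%, 2% and 5%. This is an upper bound on the chance of a pause, since an SAE arising after the tenth dose holds up nothing.

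**The case against.** The strongest reply is that oversight is not absent. Related, unexpected SAEs go to the IRB (15.2.4), which also reviews as needed and whose approval is required to continue (16.0). Participants are watched for at least 30 minutes after injection (10.4.1) and seen on Days 1 to 6, 8, 15 and 28 (11.2). Abnormal sites bring them back twice a week (11.3). Investigators monitor adverse events (16.0), and Section 14.0 provides for withdrawal. All of this stands, and a reader who infers that the trial is unmonitored goes beyond the text. These measures protect participants already dosed; none holds the next dose while the SMC considers an event.

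A reader might also infer that SMC advice will come too late. The documents do not show that. Advice on proceeding with BCG suggests review during dosing, and meeting dates may be set outside the protocol. Only the possibility is established.

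A reader might conclude that the vaccine is being used off-label. The label is not supplied, and Section 5.5 calls the dose on-label. What can be shown is a conflict between the route described as licensed and the route used.

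A further inference would be that an independent board is required. Section 5.4 cites earlier human BCG studies, including an intradermal challenge in 40 volunteers, and concludes that they support feasibility and safety. That could justify light monitoring; Section 16.0 simply does not use it.

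Finally, the example trigger is a matter of judgment and has limited sensitivity. By Section 18.1, five participants show at least one event only 23% of the time at a 5% true rate (1 − 0.95^5 = 0.226). Section 11.3 places abnormal sites around Day 28, which only three participants would have reached, or one with 30-day accrual. That is why the trigger should be left to the sponsor.

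**Conclusion.** The point holds. Both grounds for the waiver in Section 16.0 conflict with the protocol's own text: the first plainly, the second as to route and subject to a label that is not supplied. Separately, no supplied text ties an SMC review or a dosing pause to the ten BCG doses, so the number guaranteed to remain open to SMC advice is zero. Under even 60-day accrual, a first meeting on day 56 would leave one dose open and a meeting on day 84 none.

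These counts rest on assumed accrual patterns and meeting dates. They show what the text permits and do not predict what the site will do. Rewording 16.0 alone would leave oversight unchanged; the pause and the required review are the parts that change conduct. The change is worth making before enrollment, but it affects no power or efficacy figure.

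**What to change.** 1. **Sections 13.0 and 15.2.4:** after any SAE judged related, pause further BCG dosing and require prompt SMC review before it resumes. This costs nothing unless such an event occurs.
2. **Section 13.0:** require at least one SMC safety review while doses remain. One option is the fourth or fifth participant's Day 15, with the recommendation due before the eighth dose; the sponsor should choose the trigger.
3. **Section 16.0:** replace the rationale with the actual design and route, namely a randomized phase 1 challenge giving intradermally a vaccine described as licensed for percutaneous use. If light monitoring is kept, justify it by the earlier BCG studies in Section 5.4.

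The cost is a few sentences, one scheduled SMC meeting and a possible hold on the eighth dose. With the fifth-participant trigger, the hold cannot exceed 15 days plus the SMC turnaround if the visit is on time. The fourth-participant trigger suits a slower committee, at the price of less Day 28 data at the review.
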